There is a slight burden of using the technology to complete these tests, though all our participants are required to have a smart phone in order to sync their tracking devices regularly and we do not expect the level of expertise needed here is more than already required. Included in the instructions are links to short video clips demonstrating the procedures for clarity.

The participants may contact us at any time throughout the procedures.

Once testing is complete will ask the participants to send back the locked container using a pre-addressed shipping label. This can be picked up by the shipper if the participant does not feel safe. Finally, upon receipt of the materials all equipment will be sanitized with medical grade cleaners.

Blood testing. With each study visit, serum hemoglobin/hematocrit will be obtained to assess for the presence of anemia, and serum chemistries will be obtained to assess serum creatinine to identify renal dysfunction. Additionally, at baseline, 3 & 6 months, blood will be obtained for long-term storage of serum and plasma for future studies. Planned studies include assessments of markers of inflammation and CV injury.

Database management

All data management activities will be accomplished through a secure web-based Oncore application managed and administered by the CCCWFUHS (see

Improving Exercise Capacity with a Tailored Physical Activity Intervention in Lymphoma and Breast Cancer Patients Undergoing Treatment – An addendum to NIH
R01CA167821 “Early Imaging Detection of CV Injury after Cancer”
Wake Forest Baptist Comprehensive Cancer Center
CCWFU# 99112

Resources – [name], Jr.). This system allows flexibility in processing data management tasks, including the ability to register participants and verify eligibility criteria before randomization, provide the randomization assignment, and allow real-time monitoring and reporting of accrual, retention, and intervention adherence.

6.0 Analytic Plan

We will enroll 21 patients with 14 in the PAI and 7 in HLI. The goal of this study is to determine feasibility and preliminary efficacy data. We now describe these measurements.

Feasibility:

We will determine the proportion of patients who agree to participate in the intervention. Next, among patients who agree to participate we will determine what proportion are able to complete the intervention and document barriers to participation. For all patients – both in the active and control groups, we will determine the proportion who are able to have the baseline and follow-up assessments of measures of interest (cardiovascular imaging, exercise measures (peak VO₂ and 6 min walk distance).

In addition, for the patients receiving the active intervention we will assess the change in outcomes of interest to determine preliminary efficacy estimates. The control patients will also provide some preliminary efficacy assessments.

With 21 patients we can estimate a 95% exact confidence interval (using the Clopper-Pearson method) for the proportion of patients who have measurements taken with a width of 0.578 (i.e., from 0.211 to 0.789 if the observed proportion is 0.5 – most conservative assumption).

For estimating the outcomes of interest, a 95% confidence interval will extend +/- 0.769 standard deviation if there are 8 patients in the active group, +/- 0.635 if the sample size is 12 and +/- 0.554 SDs if the sample size is 15.

A number of assessments will be made on the patients enrolled. These include measures of peak exercise cardiac output, calculated A-V O₂ difference and VO₂, and pre- exercise measures of LV & cognitive function, HRQOL, six-minute walk distance (6minWD) and fatigue. For each of these measures we will calculate descriptive statistics in order to get some preliminary data concerning the mean values and variability of these measures. We will also obtain mean and variability values of the MRI cardiac function and HRQOL data from the 47 lymphoma patients in the parent study that did not undergo the two arms of the intervention as noted in this pilot addendum. This information will be helpful for designing a future clinical trial.

Improving Exercise Capacity with a Tailored Physical Activity Intervention in Lymphoma and Breast Cancer Patients Undergoing Treatment – An addendum to NIH
R01CA167821 “Early Imaging Detection of CV Injury after Cancer”
Wake Forest Baptist Comprehensive Cancer Center
CCWFU# 99112

Accrual:

It is anticipated that at least 1 patient a month will be accrued so that the total time of enrollment should be no more than 1.5 year.

Study Length:

Two years

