This study is designed to demonstrate feasibility of performing the (PAI) and the primary outcome measures before, during and six months after initiating Anth-bC or other potentially cardiotoxic cancer therapies for treatment of non- or Hodgkin lymphoma and Stages I-IV breast cancer. This study will test the potential for a novel (lifestyle) intervention designed to improve exercise capacity, HRQOL and cardiac and cognitive dysfunction. This data will inform the development of the R33 phase of the clinical trial to determine if the (PAI) can reduce exercise intolerance in this high-risk population. In addition, cardiac MRI data from individuals within this pilot will be compared to cardiac MRI data from individuals in the parent study that did not undergo either of the two interventional arms of this study.

Anthracycline-based chemotherapy (Anth-bC) or other potentially cardiotoxic cancer therapies improves cancer-related survival in non-Hodgkin lymphoma (NHL) , but Anth-bC or other potentially cardiotoxic cancer therapies also can promote left ventricular (LV) dysfunction, exercise intolerance, fatigue, reduced health-related quality of life (HRQOL) and cognitive impairment threatening observed gains in cancer survivorship.¹⁻³

- Prospective analyses show that ~20% of patients with NHL taking Anth-bC experience >10% reductions in LVEF ($p<0.0001$) and reduction in peak exercise capacity (VO_2) to <80% of pretreatment values⁴⁻⁶
- Lymphoma survivors experience marked reductions in HRQOL and often require psychosocial support interventions to perform societal activities of daily living. Routine exercise enhances both physical and mental HRQOL in survivors of lymphoma.⁶⁻⁸
- Cognitive impairment occurs after receipt of Anth-bC for NHL. Breast cancer recipients of doxorubicin experience cognitive dysfunction that improves as activity levels increase.⁹

In cancer survivors, exercise capacity – a modifiable characteristic that is strongly associated with risk of CV events – is reduced after Anth-bC or other potentially cardiotoxic cancer therapies can be enhanced through exercise training, and is associated with improved QOL and cognitive function.

- Survey data suggest that more physical activity after lymphoma is associated with decreased CV events.¹⁰

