2.0 Objectives

2.1 Primary Objective

To provide critical participant enrollment data necessary to accomplish the R01 submission, including:

- 2.1.1 Feasibility of screening, enrolling, and randomizing 21 Non or Hodgkin lymphoma and stage I-IV breast cancer patients including the reasons for failed randomization,
- 2.1.2 Identification of barriers for participating in, or adhering to the Patient ES-AI and the Healthy Living Control Group.

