participants who need additional reminders and/or counseling, and gain insight to difficulty with participation in PAI. Interventionists first meet with each participant to discuss expectations and negotiate participant goals. Interventionists then use a flexible “toolbox” approach to tailor interventions to each participant’s needs. Using a social problem-solving framework, a problem is identified (e.g., fatigue), and a solution is found (e.g., negotiate alternate time when energy is higher) and tested for a specific period of time (e.g., 2 sessions). Participants have input on options that are selected. If the solution effectively resolves the problem, the strategy is continued until consistent behavior change is observed. If the solution is unsuccessful, a new option for solving the problem is selected (e.g., decrease intensity of physical movements) and tested. Collectively, these strategies will increase social cognitive mechanisms for regular participation and enhanced adherence in both groups. Our team has had remarkable success with this approach, exceeding study goals for adherence and retention in several federally-funded trials of physical movement-based interventions in adults with chronic disease, e.g., cancer.

Healthy Living Control Group (Arm 2)

Those participants randomized to the control arm will come to a centralized meeting location or receive an invitation for an online meeting to participate in organized health workshops. Each session will last 60 minutes and match the number of visits to the rehab centers for the PAI in a 1:1 fashion with 2 sessions offered per month on Reynolda Campus and remaining sessions over the telephone over the 6 months. (Table 4). Make up sessions either in person or over the telephone will be offered for those participants who have to miss a group session. It is the objective of this HLI intervention to match participant contact with the PAI.

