Session Content: Introduction and Review past material (10 mins); Interactive Healthy Living Presentation (30 mins); Short instructor-led program of upper body stretching exercises (10 mins); Wrap-Up & discussion of next Workshop (10 mins). The topic list is shown Table 5. The purpose of the “Healthy Living” study arm is to control for attention from study staff and social interaction in the intervention group. The design of the control group was informed by the following principles; 1) to positively impact recruitment, participant interest in participation, and on-going adherence to the healthy living arm of study; 2) to have a comparison group that does not directly influence the primary outcome; and 3) to provide a program that would offer benefit to the study participant. There is no evidence to suggest that health education alone will impact physical activity participation or exercise capacity. In addition, the decision to use a once

Improving Exercise Capacity with a Tailored Physical Activity Intervention in Lymphoma and Breast Cancer Patients Undergoing Treatment – An addendum to NIH
 R01CA167821 “Early Imaging Detection of CV Injury after Cancer”
 Wake Forest Baptist Comprehensive Cancer Center
 CCCWFU# 99112

per week schedule was based on careful review of science, adherence, and expense considerations and the request to match the number of interventions in the HLI group with the once per week minimum cardiac rehabilitation center visits received by the PAI participants. Note that participants will receive referrals to exercise facilities at study completion (Table 4).

The Healthy Living presentations will be interactive and will provide useful information on such topics as proper nutrition, management of stress, and sleep practices (Table 5). Experts (we have used from prior studies across a broad range of relevant topics will be brought in to give guest lectures over the course of the 6 months. Participants will be asked to complete homework assignments, review past topics, and engage in small group discussions as a means to increase active involvement in this study arm. The final component of the workshop, the upper body stretching component, was chosen to be part of the control arm to enhance adherence to this arm of the study. Specifically, this “placebo exercise” activity will serve to increase the benefit perceived by the participants of the workshops without directly affecting the study outcomes.

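### Preliminary efficacy is taken from change within the PAI arm; no PAI-minus-HLI difference is defined although patients are randomised 14 to 7

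*Combined protocol and SAP*

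**What the plan says.** Section 6.0 gives the study two aims: "The goal of this study is to determine feasibility and preliminary efficacy data". For the second it states that "for the patients receiving the active intervention we will assess the change in outcomes of interest to determine preliminary efficacy estimates". The control arm gets one sentence: "The control patients will also provide some preliminary efficacy assessments". Beyond that, the plan is descriptive statistics for each measure, plus means and variability from 47 parent-study patients.

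The precision for outcomes is given as 95% half-widths of 0.769 SD "if there are 8 patients in the active group, +/- 0.635 if the sample size is 12 and +/- 0.554 SDs" for 15. None of these sample sizes is the planned 14.

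The design is randomised. Section 2.1 lists "Feasibility of screening, enrolling, and randomizing 21 Non or Hodgkin lymphoma and stage I-IV breast cancer patients", Section 4.3 says "Those participants randomized to the control arm will come to a centralized meeting location", and Section 6.0 gives the split as 14 PAI and 7 HLI. One stated principle behind the HLI arm in Section 4.3 is "to have a comparison group that does not directly influence the primary outcome". Section 1.0 adds: "This study will test the potential for a novel (lifestyle) intervention designed to improve exercise capacity".

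No section defines a difference between PAI and HLI, or an interval for one. The only between-group comparison stated is in Section 1.0: cardiac MRI in this pilot against parent-study patients, which is not randomised.

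**The concern.** The programme described in Section 1.0 is meant to prevent declines during treatment, and the same section expects declines without it: about 20% of NHL patients on anthracyclines lose more than 10% of LVEF and fall in peak VO2. With a preventive aim, success may look like no change, or a smaller fall, in the PAI arm. Change within that arm cannot tell this apart from an ineffective programme. If controls decline, within-PAI change understates or hides the effect; if controls improve, it overstates it.

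Section 1.0 also cites 301 women in whom exercise did not prevent a decline in peak VO2. A fall seen in an exercise arm alone would not show whether exercise slowed it. The HLI arm can separate these possibilities, and the plan does not say it will be used to do so. The estimates are meant to inform the next trial, so a misleading one would carry forward.

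**Working it through.** **1. The plan's own precision (Section 6.0).** One-sample half-width in SD units = t(0.975, n−1)/√n.

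| n | Computed | Stated |
|---|---|---|
| 8 | 2.365/2.828 = 0.836 | 0.769 |
| 9 | 2.306/3 = 0.769 | not stated |
| 12 | 2.201/3.464 = 0.635 | 0.635 |
| 14 | 2.160/3.742 = 0.577 | not stated |
| 15 | 2.145/3.873 = 0.554 | 0.554 |

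The figures for 12 and 15 reproduce, which confirms a single-arm basis. The figure given for 8 is the value for 9.

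**2. What within-arm change estimates.** Expected PAI change = intervention effect + change that would occur anyway. With an assumed effect of +0.5 SD, a background change of −0.5 SD gives an expected PAI change of 0, −1.0 SD gives −0.5 SD, and +0.5 SD gives +1.0 SD.

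**3. Illustration from the 20-patient trial cited in Section 1.0.**
- Exercise arm +2.6, non-exercisers −1.5 ml/min/kg. Difference: 2.6 − (−1.5) = 4.1. Within-arm change misses 1.5, or 1.5/4.1 = 37%.
- The control change is imprecise. Assuming 10 per arm and that 2.2 is an SD: −1.5 ± 2.262 × 2.2/√10 = −1.5 ± 1.57, i.e. −3.07 to +0.07.
- The split is not stated. If there were 20 non-exercisers: −1.5 ± 2.093 × 2.2/√20 = −1.5 ± 1.03, i.e. −2.53 to −0.47.

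**4. Precision of PAI minus HLI in this study.** Inputs: 14 and 7 from Section 6.0; complete data and equal variances assumed. √(1/14 + 1/7) = 0.463. Results are in SDs of the outcome.
- Unadjusted: t(19) × 0.463 = 2.093 × 0.463 = 0.969.
- Baseline-adjusted: t(18) × √(1−r²) × 0.463, where r is the baseline-to-follow-up correlation. The documents give no r, so a range is shown.

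| | r = 0.5 | r = 0.7 | r = 0.8 |
|---|---|---|---|
| Adjusted, 14 vs 7 | 0.842 | 0.695 | 0.584 |
| Same × √(1 + 1/17) = 1.029, for chance baseline imbalance | 0.867 | 0.715 | 0.600 |
| Adjusted, 12 vs 6 evaluable (assumed), t(15) × 0.5 × √(1−r²) | 0.923 | 0.761 | 0.639 |

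Unadjusted at 12 vs 6: t(16) × 0.5 = 1.060.

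**5. Price compared with within-PAI change (n = 14).** The SD of change is √(2(1−r)) outcome SDs, so the half-width is 0.577 × √(2(1−r)) = 0.577, 0.447 and 0.365 at r = 0.5, 0.7 and 0.8. The adjusted difference is therefore 1.46, 1.55 and 1.60 times as wide.

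If the cited trial's change SDs (3.7 and 2.2) held here, the unadjusted difference in change would have a Welch half-width of 2.71 ml/min/kg (18.2 df), against 2.160 × 3.7/√14 = 2.14 within PAI, a ratio of 1.27.

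**The case against.** The strongest reply is that efficacy is not an objective. Section 2.1 concerns enrolment and barriers, Section 2.2 the ability to obtain the measures, and Section 5.1 makes feasibility primary. Controls are not ignored either: Section 6.0 gives them a sentence, its descriptive statistics cover all enrolled patients, and arm-level summaries would let a reader subtract. With 7 controls the difference will be imprecise whatever model is used.

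Much of this stands and limits the weight of the point. But Section 6.0 itself makes preliminary efficacy a goal and says which quantity will represent it. The sentence on controls defines no contrast, and the descriptive statistics are not said to be by arm. Imprecision is a reason for an interval without a test. It does not make a narrower interval around a different quantity the better efficacy estimate.

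Three further cautions are fair. The cited trial is a 12-week cycling programme with an unstated split, so it only illustrates. Section 5.2 calls peak VO2 the primary outcome measure while Section 5.1 names feasibility, so peak VO2 can lead only among the efficacy measures. And the home test battery in Section 5.2 includes no CPET or MRI, so the complete-data precision is a best case.

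**Conclusion.** The concern holds. As written, the preliminary efficacy estimate mixes the intervention effect with change under cancer therapy, and the randomised control arm that could separate them has no defined role in it. The size of the distortion in this study is unknown. In the cited trial it was 1.5 of 4.1 ml/min/kg, with an interval from about nil to 3.1 under the 10-per-arm assumption.

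The point should be corrected. It does not touch the primary feasibility outcome. The precision figures for the difference rest on complete data, equal variances and assumed correlations. The wrong half-width for n = 8 is a separate arithmetic slip, and the conclusion does not depend on it.

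**What to change.** State in Section 6.0 that preliminary efficacy is the PAI-minus-HLI difference at 3 and at 6 months, analysed as randomised, from a linear model of the follow-up value on arm and baseline value, reported with a 95% CI and no hypothesis test. Peak VO2 leads the efficacy measures and the others are supportive. Within-arm changes and the non-randomised parent-study comparison are descriptive only.

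Give the matching expected half-width for 14 vs 7 with its assumptions: about ±0.97 SD unadjusted, or ±0.84, 0.69 or 0.58 SD adjusted at correlations of 0.5, 0.7 or 0.8, and about 3% wider allowing for chance baseline imbalance. If the single-arm figures stay as descriptive precision, correct n = 8 to 0.836. Naming a lead visit and a rule for missing measurements would be useful but optional detail.

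The cost is plan wording and one simple model per measure and visit, on data already collected in both arms. Visits and sample size do not change. The price is a wider interval than for within-PAI change: about 1.5 to 1.6 times with equal variances, or about 1.3 times if the cited trial's unequal SDs applied.

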5.0 Outcome Measures

5.1 Primary Outcome

5.1.1 The primary outcome will be feasibility. The data gathered will be used to inform the development of a larger future study. Feasibility

in this study will be defined as follows: the proportion of patients who agree to participate in the intervention. Among patients who agree to participate the proportion that are able to complete the intervention and document barriers to participation.

5.1.2 For all patients – both in the active and control groups, we will determine the proportion who are able to have the baseline and follow-up assessments of measures of interest (cardiovascular imaging, exercise measures (peak VO₂ and 6 min walk distance).

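### The assessment-completion proportion is planned as one figure for all 21 patients, so by itself it cannot show whether follow-up differs between the exercise and control arms

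*Combined protocol and SAP*

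**What the plan says.** Section 5.1.1 states "The primary outcome will be feasibility". Section 5.1.2 adds a component on data collection: "For all patients – both in the active and control groups, we will determine the proportion" able to have the baseline and follow-up assessments, namely cardiovascular imaging, peak VO₂ and 6-minute walk distance.

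Section 6.0 repeats this: "we will determine the proportion who are able to have the baseline and follow-up assessments of measures of interest". It sets the sample ("We will enroll 21 patients with 14 in the PAI and 7 in HLI") and then gives one precision statement for this outcome. That statement begins "With 21 patients we can estimate a 95% exact confidence interval", continues "using the Clopper-Pearson method) for the proportion of patients who have measurements taken", and ends "with a width of 0.578 (i.e., from 0.211 to 0.789 if the observed proportion is 0.5".

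No section states this proportion, or an interval for it, separately for PAI and HLI. The only arm-specific precision in Section 6.0 concerns continuous outcomes in the active group. The database text in Section 5.2 mentions reporting of retention, without reference to arm. Visit times come from Section 5.2.1: first visit, 3 months and 6 months.

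**The concern.** The pilot is meant to inform a larger randomised trial. In such a trial, outcome data that are missing to a different extent in the two arms can bias the comparison, so the pilot should show how well assessments were obtained in each arm.

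A single proportion over both arms averages the two, with two thirds of the weight on PAI. A reassuring pooled value can coexist with poor follow-up of the 7 controls, and a middling one can hide whether the shortfall lies in one arm or in both.

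**Working it through.** **Inputs.** From Section 6.0: n = 21, 14 PAI, 7 HLI, 95% confidence, Clopper-Pearson method, printed interval 0.211 to 0.789 (width 0.578) at an observed proportion of 0.5. The completion counts below are assumed for illustration, because the documents give no expected completion or dropout rate.

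**Formula.** For x of n, the lower limit is the 0.025 quantile of Beta(x, n − x + 1) and the upper limit is the 0.975 quantile of Beta(x + 1, n − x).

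**Step 1: the plan's own interval.** It does not reproduce at n = 21.
- 10/21: 0.257 to 0.702, width 0.445.
- x = 10.5 (exactly one half, not an attainable count): 0.277 to 0.723, width 0.445.
- 6/12: 0.2109 to 0.7891, width 0.5781, which matches the printed values. In a search over n = 7 to 24, only n = 12 matches.

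The printed interval is therefore labelled for 21 patients but carries the numbers for 12. This error is separate from the by-arm question, which does not depend on it.

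**Step 2: how the arms combine.** Pooled proportion = (14/21) × PAI proportion + (7/21) × HLI proportion. With 17 of 21 assessed:
- 14/14 and 3/7: 0.667 × 1 + 0.333 × 0.429 = 0.810.
- 10/14 and 7/7: 0.667 × 0.714 + 0.333 × 1 = 0.810.

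**Step 3: every split that gives 17/21.** The pooled exact interval is 0.581 to 0.946 in every row.

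| PAI | exact 95% CI | HLI | exact 95% CI | Fisher two-sided p |
|---|---|---|---|---|
| 14/14 (100%) | 0.768 to 1 | 3/7 (43%) | 0.099 to 0.816 | 0.006 |
| 13/14 (93%) | 0.661 to 0.998 | 4/7 (57%) | 0.184 to 0.901 | 0.088 |
| 12/14 (86%) | 0.572 to 0.982 | 5/7 (71%) | 0.290 to 0.963 | 0.574 |
| 11/14 (79%) | 0.492 to 0.953 | 6/7 (86%) | 0.421 to 0.996 | 1.00 |
| 10/14 (71%) | 0.419 to 0.916 | 7/7 (100%) | 0.590 to 1 | 0.255 |

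The p-values only indicate how far apart the arms are in each row; they are not a proposed analysis. The HLI proportion runs from 43% to 100% with no change in the pooled figure or its interval.

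**Step 4: what by-arm reporting can deliver.** Near one half, 7/14 gives 0.230 to 0.770 (width 0.539) and 3/7 gives 0.099 to 0.816 (width 0.717). These widths support description, not a test.

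**The case against.** **The wording does not rule out a split.** The phrase naming both groups can be read as setting who is counted, or loosely as meaning each group, and the sentence on 21 patients is a precision statement, not a table specification. This stands in part: the plan does not forbid a by-arm split. But the text gives one proportion, for all patients, with one interval at the combined sample size, so pooling is the plain reading. If a split was intended, the same edit would make it explicit.

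**Other parts of the plan would reveal arm differences.** Section 2.1.2 asks for barriers in both the activity and the control group, Appendices L and M are separate programme evaluations, and Section 4.3 gives all HLI patients qualitative assessment. This also stands in part. These sources would partly distinguish the pilots in the table, but none specifies the share of each arm with imaging, peak VO₂ or walk distance obtained.

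**Stronger readings to avoid.**
- A reader might infer that the two programmes create different incentives to return. The documents do not say so. Section 4.3 aims to match HLI contact to PAI, expects its strategies to improve adherence in both groups, and chose control content to support adherence; Table 4 shows both arms at every contact level. Unequal follow-up is possible, but the documents do not predict it.
- A reader might infer that very different pilots would lead to the same conclusion. The plan sets no feasibility threshold or decision rule, so it specifies no conclusion, and the other feasibility components would differ.
- A reader might infer from 10/14 against 7/7 that the exercise arm is losing patients. The intervals overlap widely and Fisher's p is about 0.25, so those counts would not establish differential loss.

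**Seven controls are too few.** This is true for testing or for excluding a difference. Counts with reasons for missing data are still useful for design.

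**Conclusion.** The point holds as a reporting gap in one component of the primary outcome. As written in Sections 5.1.2 and 6.0, the assessment-completion figure cannot by itself show follow-up that differs by arm. At 17/21 it is compatible with HLI completion anywhere from 3/7 to 7/7.

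This rests on the plain reading of the text as pooled, on all 21 patients being enrolled 14:7 and kept in the denominator, and on illustrative counts. It is not evidence that follow-up will differ, nor that the pilot as a whole would miss a difference. It is a cheap improvement to a descriptive pilot. The mislabelled interval in the same paragraph is a plain numerical error: the width at 21 patients is about 0.445, not 0.578.

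**What to change.** 1. In Sections 5.1.2 and 6.0, state that the count and proportion with each measure obtained (imaging, peak VO₂, 6-minute walk) will be reported by randomised arm, as x/14 PAI and y/7 HLI, at baseline, 3 months and 6 months. Add Clopper-Pearson intervals and reasons for missing assessments, beside the pooled figure. Say that this is descriptive and that no between-arm test is planned.
2. In the precision paragraph of Section 6.0, replace the printed pooled interval with the one for 21 patients, about 0.26 to 0.70 for 10/21 (width about 0.445). Add the by-arm widths near one half: about 0.54 for 14 patients and 0.72 for 7.

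The cost is a few table rows and a few sentences, with no extra patients or data collection. Three measures at three visits in two arms make 18 by-arm proportions. Their intervals will be wide, above all in the control arm, and should be read as such.

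### The 95% exact interval quoted for 21 patients (width 0.578) is the one for 6 out of 12; with 21 patients the width cannot exceed 0.445

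*Combined protocol and SAP*

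**What the plan says.** Section 6.0 sets the enrolment: "We will enroll 21 patients with 14 in the PAI and 7 in HLI". Under Feasibility it names the quantity to be estimated: "For all patients – both in the active and control groups, we will determine the proportion who are able to have the baseline and follow-up assessments". Section 5.1.2 gives the same definition as part of the primary outcome.

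The precision statement follows. It begins "With 21 patients we can estimate a 95% exact confidence interval (using the Clopper-Pearson method" and continues "with a width of 0.578 (i.e., from 0.211 to 0.789 if the observed proportion is 0.5". The plan describes 0.5 as the most conservative choice.

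The next sentence turns to continuous outcomes and gives half-widths in standard deviations for active-group sizes of 8, 12 and 15, among them "0.635 if the sample size is 12". No other section restates or corrects the interval for the proportion.

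**The concern.** The sentence fixes every input needed to check it: 21 patients, 95% confidence, the Clopper-Pearson method and an observed proportion of 0.5. A width of 0.578 looks too large for 21 patients.

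Feasibility is the primary outcome, and there is no hypothesis test or power calculation. Stated precision is therefore all the plan offers on what the sample can deliver, and this is its only such statement for a proportion. If it is wrong, anyone using the plan to judge the pilot, or to plan the larger study it is meant to inform, has the wrong idea of how well 21 patients estimate this proportion.

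**Working it through.** **Inputs**, all from Section 6.0:
- n = 21, covering both arms.
- 95% two-sided, so 0.025 in each tail.
- Clopper-Pearson method.
- Observed proportion 0.5.

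**Formula.** For x successes in n, with B(q; a, b) the q-quantile of the beta distribution:
- lower limit = B(0.025; x, n − x + 1)
- upper limit = B(0.975; x + 1, n − x)

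**Step 1: find the count that gives the stated figure.** The plan's three numbers agree with one another: 0.789 − 0.211 = 0.578, symmetric about 0.5. A garbled digit is therefore unlikely. They are reproduced by x = 6, n = 12:
- lower = B(0.025; 6, 7) = 0.2109
- upper = B(0.975; 7, 6) = 0.7891
- width = 0.5781

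Over every count for n from 5 to 30, only 6/12 gives a width within 0.0006 of 0.578. The neighbouring sample sizes at x = n/2 do not fit: n = 11 gives 0.200 to 0.800 and n = 13 gives 0.221 to 0.779.

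**Step 2: apply the stated inputs.** A proportion of exactly 0.5 cannot occur with 21 patients, so the two nearest counts are shown with the interpolated value.

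| x/n | Lower | Upper | Width |
|---|---|---|---|
| 10/21 | 0.2571 | 0.7022 | 0.4451 |
| 11/21 | 0.2978 | 0.7429 | 0.4451 |
| 10.5/21 (not attainable) | 0.2773 | 0.7227 | 0.4455 |

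Over x = 0 to 21 the largest width is 0.4451, at x = 10 and x = 11. As a check, the binomial tail probability is 0.025 at each limit for both 6/12 and 10/21.

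**Step 3: size of the discrepancy.** 0.578 − 0.445 = 0.133, and 0.578 / 0.445 = 1.30.

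**Step 4: other readings that might rescue the figure.**

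| Reading | Width |
|---|---|
| PAI arm only, 7/14, Clopper-Pearson | 0.539 |
| HLI arm only, n = 7, Clopper-Pearson | about 0.72 |
| n = 21, 99% Clopper-Pearson | 0.552 to 0.553 |
| n = 21, 99.5% Clopper-Pearson | 0.589 to 0.590 |
| n = 21, Wald | 0.427 to 0.428 |
| n = 21, Wald with continuity correction | 0.475 |
| n = 21, Wilson | 0.393 |

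None gives 0.578.

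**The case against.** The strongest reply concerns weight, not arithmetic. The error is conservative, since the study will be more precise than stated. The plan sets no feasibility threshold, go/no-go criterion or precision target that depends on 0.578, and it does not derive the enrolment of 21 from the interval. The reported interval will be computed from the observed count, so the wrong planning figure cannot carry into the results. All of this stands, and it limits the consequence to a misleading planning statement.

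A second reply is that 12 evaluable patients may have been meant. The text does not support this. Section 6.0 gives no dropout rate or evaluable subset. Patients who miss their assessments count as failures in this proportion, so they stay in its denominator. The number 12 appears in the section only as a scenario for continuous outcomes.

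One caution also stands. The match with 6/12 identifies what the numbers are, not how they got there. The documents do not say whether they were carried over from a smaller plan.

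**Conclusion.** The stated interval is wrong for the stated sample size. With 21 patients the 95% Clopper-Pearson interval for this proportion is at most 0.445 wide, against 0.578 in the plan: an overstatement of 0.133, or about 30%. The conclusion rests only on inputs in the sentence itself and on the definition in Section 5.1.2, which makes all 21 patients the denominator. It needs no outside assumption.

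The sentence should be corrected because it is the only precision figure for a proportion and it describes a primary-outcome component. The error does not undermine the sample size, the analysis or the conduct of the study.

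**What to change.** Replace the precision sentence in Section 6.0 with wording such as:

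> For the proportion of the 21 patients with measurements taken, the 95% Clopper-Pearson interval is at most 0.445 wide (for example, 0.257 to 0.702 if 10 of 21 have them).

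Using 10/21 also avoids an observed proportion that 21 patients cannot produce. If the authors did intend a denominator of 12, they should say so, explain who the 12 are and keep 0.211 to 0.789. That would also mean reconciling the sentence with the all-patients definition in Section 5.1.2.

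As an optional addition, any proportion reported for the 14 PAI patients alone has a maximum width of about 0.54 (0.230 to 0.770 for 7/14).

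The cost is one sentence, with no change to sample size, conduct or analysis.
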